3.1 Subjects

Healthy infants with age ≥ 2 months and < 43 months (recommended age in months: ≥ 2 months and < 7 months)

3.2 Inclusion Criteria

Subjects meeting all of the following inclusion criteria at the time of the first vaccination of the investigational product will be eligible for study participation.

- (1) Healthy infants aged ≥ 2 months and < 43 months (recommended ≥ 2 months and < 7 months) at the time of the first vaccination with the investigational product. However, although persons meeting the following definition of “persons who should receive a vaccination with care” may participate in the study, whether or not to enroll them in the study should be decided carefully.
- (2) Persons from whose legal guardians written consent to study participation has been obtained.

Persons Who Should Receive A Vaccination With Care

- 1) Persons who clearly have underlying diseases, such as cardiovascular disease, kidney disease, liver disease, blood disease, respiratory disease, or a developmental disorder
- 2) Persons who have developed a pyrexia within 2 days after receiving a vaccination in the past
- 3) Persons with a past history of convulsions

Rationale

- (1) This inclusion criterion was established in accordance with the “Routine Immunization for Hib Infection” section in the Routine Immunization Guidelines. The timing of the start of immunization with DPT-IPV was established taking into account the fact that, at the Sixth Health Science Council Immunization/Vaccine Committee’s Research and Development and Production/Distribution Subcommittee (held November 28, 2013),¹⁰⁾ it was announced that investigations into the development of a combined vaccine that included DPT-IPV would proceed with an eye towards making the timing of the first vaccination of the vaccine the same as that for the Hib vaccine. In addition, as far as the upper limit of vaccination age in months is concerned, if the vaccination interval is maximized (the second dose is administered 8 weeks after the first dose, the third dose is administered 8 weeks after the second dose, and the fourth dose is administered 13 months after the third dose, for a total period of 17 months), then in order to complete the administration of the fourth dose of the investigational product while the subjects are still younger than 60 months of age, the target age for routine Hib immunization, the subjects who can be enrolled into the study must be younger than 43 months of age. Furthermore, the recommended age for study entry was set as ≥ 2 months and < 7 months, because this is the target population for the fourth dose of the Hib vaccine in routine immunization.

Persons Who Should Receive A Vaccination With Care

The persons who should receive a vaccination with care, as defined in 1) through 3) above, were established in accordance with the Immunization Act Enforcement Regulations and the Immunization Guidelines.

- (2) The legal guardians are defined as the parents, in accordance with the “Guidance on Clinical Studies of Drug Products in Pediatric Populations”¹²⁾ (PFSB/ELD Notification No. 1334, dated December 15, 2000).

3.3 Exclusion Criteria

Subjects meeting any of the following exclusion criteria at the time of the first vaccination with the investigational product will be excluded from study participation.

- (1) Persons who have received diagnoses of immunodeficiencies in the past, or who are currently receiving treatments that cause immunosuppression
- (2) Persons with close relatives (up to third degree of kinship) who have a congenital immunodeficiency
- (3) Persons who might experience a serious allergy in response to a food, drug product, etc.
- (4) Persons with thrombocytopenia and/or coagulation disorders, or persons receiving treatments that inhibit platelet aggregation or blood coagulation
- (5) Persons who have had Hib infections, pertussis, diphtheria, tetanus, or acute poliomyelitis in the past
- (6) Persons who have received a vaccination against Hib, pertussis, diphtheria, tetanus, or polio in the past
- (7) Persons who have received live vaccines within 27 days, or inactivated vaccines/toxoids within 6 days, before the first vaccination with the investigational product
- (8) Persons who have received blood transfusions, immunosuppressants (except for topical drugs), or immunoglobulin preparations (including HB immunoglobulin preparations and monoclonal antibodies [e.g., Synagis, palivizumab])
- (9) Persons who have received corticosteroids (except for topical drugs) at a prednisolone dose level equivalent of 2 mg/kg/day or higher
- (10) Persons who have participated in another clinical study and received another investigational product within 12 weeks before obtaining informed consent
- (11) Persons who were less than 37 weeks old at birth, or who weighed less than 2500 g at birth
- (12) Persons otherwise judged to be unsuitable for participation in this study by the (sub)investigator

Rationale

- (1)(2)(5)(6)(8)(9) These criteria were established because these conditions could affect efficacy and safety.
- (3) This criterion was established with safety in mind, and in accordance with the Immunization Act Enforcement Regulations and the Routine Immunization Guidelines.
- (4) This criterion was established for safety considerations.
- (7) This criterion was established in accordance with the vaccination interval in the Routine Immunization Guidelines.
- (10) This criterion was established to ensure that this study is conducted ethically, and also because the effects on efficacy and safety of drugs that have not been properly evaluated are unpredictable.
- (11)(12) These criteria were established to ensure that this study is conducted safely and ethically.

3.4 Vaccination Postponement Criteria

- (1) If the subject clearly has a pyrexia (if the patient's temperature is $\geq 37.5^{\circ}\text{C}$ immediately before vaccination)
- (2) If the subject has clearly developed a severe, acute illness
- (3) If the (sub)investigator determines for some other reasons that it would not be appropriate for the subject to receive a vaccination

Rationale

These criteria were established in accordance with the Immunization Act Enforcement Regulations and the Routine Immunization Guidelines.

4. Explanation and Consent

4.1 Preparation of Subject Explanation Sheet and Informed Consent Form

The principal investigator will prepare an explanation sheet for legal guardians and informed consent form (explanation sheet/informed consent form). The explanation sheet/informed consent form will be prepared as a single, unified document, and will be revised as needed.

The prepared or revised explanation sheet/informed consent form will be submitted to the study sponsor and approved by the institutional review board prior to the start of the study.

4.2 Information That Should be Included in the Explanation Sheet

The explanation sheet must include the following information at a minimum.

- (1) The fact that the study has an experimental aspect
- (2) The objectives of the study
- (3) The names, job titles, and contact information for the principal investigators and subinvestigators
- (4) Study method (including the experimental aspects of the study, the subject inclusion criteria and, if randomization is being performed, the probabilities of the patient being assigned to each treatment)
- (5) The expected clinical risks and benefits (If there are no expected benefits to the subject, then this must be explained to the legal guardians.)
- (6) Whether or not there are other preventive therapies that are available to the subjects
- (7) The planned term of participation in the study
- (8) The fact that participation in the study is entirely up to the legal guardian, and that the legal guardian may refuse to participate in the study or withdraw from the study at any time, and that the subject will not be subject to any discriminatory treatment because of the legal guardian's refusal to participate in or withdrawal from the study, nor will not participating in the study cause the subject to lose any benefits that the subject would have been expected to receive.
- (9) The fact that the monitors, auditors, institutional review board, and regulatory authorities will be able to access the subject's medical records (source documents), and that in the case of said access the subject's privacy will be protected Also, the fact that by affixing his or her sign or sealing on the informed consent form the legal guardian consents to said access
- (10) The fact that the subject's privacy will be protected even if the results of the study are published
- (11) Whom the legal guardian should contact at the study site if the legal guardian wants to obtain information about the study or the subject's rights or to report any health injury that is related to the study
- (12) The compensation and treatment that the subject will be able to receive if the subject suffers any health injury related to the study
- (13) Information about the types of institutional review boards that will review, for example, the appropriateness of this study, what issues will be reviewed by each institutional review board, and other information about the institutional review boards that are involved in this study
- (14) The planned sample size for the study
- (15) The fact that the legal guardian will be notified promptly if any information that could affect the legal guardian's willingness to continue participating in the study
- (16) The conditions or reasons that would cause the subject's participation in the study to be discontinued
- (17) If participating in the study will impose any financial burden on the legal guardian, the exact nature thereof
- (18) If the legal guardian will receive any financial compensation for participating in the study, the exact

nature thereof (e.g., agreement on how the payments will be calculated)

(19) The rules the legal guardian will be expected to follow

4.3 Method of Obtaining Consent

Because the subjects of this study are infants, written consent will be obtained not from the subjects themselves but from the subjects' legal guardians. A legal guardian is defined as the person with parental rights for the subject in question (i.e., the father or mother).

- (1) Before initiating the study, the (sub)investigator will provide the legal guardian with an explanation sheet/informed consent form that has been approved by the institutional review board and explain its contents thoroughly to the legal guardian. A clinical research coordinator may also provide a supplemental explanation. The (sub)investigator will provide the explanation based on the explanation sheet using as simple language as possible to make sure that the legal guardian understands, and must provide adequate responses to the legal guardian's questions. The (sub)investigator will confirm that the legal guardian has thoroughly understood the explanation before obtaining the legal guardian's written consent to have the subject participate voluntarily in the study.
- (2) The (sub)investigator who provides the explanation and the legal guardian will affix their own names and seals or signatures on the consent form, and also date it. If a clinical research coordinator provides a supplementary explanation, that clinical research coordinator will also affix his or her sign or seal on the document and date it.
- (3) The (sub)investigator will, before the subject starts participating in the study, provide the explanation sheet/informed consent form with the names, seals or signatures, and dates to the legal guardian and store the original informed consent form properly, in accordance with the rules of the study site.
- (4) The date of informed consent obtainment will be recorded on the case report form.

4.4 Informed Consent Form/Subject Explanation Sheet Revision

- (1) If new, important information is obtained that could pertain to the legal guardian's consent, the (sub)investigator will promptly convey this information orally to the legal guardian and check whether or not the subject will continue participating in the study, and will record the results in the subjects' medical records.
- (2) The principal investigator will promptly determine based on this information whether or not the informed consent form/explanation sheet needs to be revised.
- (3) If the principal investigator determines that the informed consent form/explanation sheet needs to be revised, the principal investigator will do so promptly, and must then once again have it approved by the institutional review board.
- (4) The (sub)investigator will provide the legal guardian with an explanation using the explanation sheet/informed consent form that has been newly approved by the institutional review board, and will obtain the legal guardian's written consent to voluntarily continue having the subject participate in the study.
- (5) Similar to when consent is initially obtained, the (sub)investigator who provided the explanation and the legal guardian will affix their signs or seals on the revised explanation sheet/informed consent form, and date it. If a clinical research coordinator provides a supplementary explanation, that clinical research coordinator will also affix his or her sign or seal on the document and date it.
- (6) The (sub)investigator will provide the legal guardian the explanation sheet/informed consent form with the names, seals or signatures, and dates, and will retain the original of the informed consent form properly, in accordance with the rules of the study site.

5. Study Design

5.1 Study Phase and Type

[figure not shown]
Phase of the study: 3

Type of study: Exploratory

5.2 Study Design

5.2.1 Study Design

Open-label, uncontrolled, multicenter study

The following investigational products will be administered.

- BK1310: A single dose of 0.5 mL (that contains 10 µg of Hib antigen as the oligosaccharide)

For the primary immunization, subjects will receive 3 doses of investigational product intramuscularly (into the thigh), 0.5 mL for each dose, at intervals of 3 to 8 weeks (standard vaccination interval: 4 weeks). For the booster immunization, subjects will receive a single dose of investigational product intramuscularly (into the thigh) at 6 to 13 months after the primary immunization. However, the repeated vaccination with investigational product at the same location as that which was used for the previous dose will be avoided.

Rationale

The amount of Hib antigen in the investigational product has been set at 10 µg through a comprehensive determination made on the basis of, among other information, the results obtained after the administration of the third dose of the investigational product in Cohort 1 (after the completion of the primary immunization) in ongoing study BK1310-J01.

Because there do not appear to be any major differences in immunogenicity or tolerability between

intramuscular administration and subcutaneous administration, this study has been designed as an exploratory, uncontrolled study.

5.3 Endpoints

5.3.1 Efficacy Endpoints

(1) Primary endpoint

The anti-PRP antibody seroprotection (antibody titer $\geq 1 \mu\text{g/mL}$) rate, and the seroprotection rates for pertussis, diphtheria toxin, tetanus toxin, and attenuated polio virus at 4 weeks after the primary immunization

(2) Secondary Endpoints

- 1) The anti-PRP antibody seroprotection (antibody titer $\geq 0.15 \mu\text{g/mL}$) rate and the geometric mean antibody titer for anti-PRP antibodies at 4 weeks after the primary immunization
- 2) The anti-PRP antibody seroprotection (antibody titer $\geq 1 \mu\text{g/mL}$) rate, at a concentration of $1 \mu\text{g/mL}$ or above, and the anti-PRP antibody seroprotection (antibody titer $\geq 0.15 \mu\text{g/mL}$) rate and the geometric mean anti-PRP antibody titer for anti-PRP antibodies at 4 weeks after the booster immunization.
- 3) The geometric mean antibody titers for pertussis, diphtheria toxin, tetanus toxin, and attenuated poliovirus at 4 weeks after the primary immunization
- 4) The antibody seroprotection rates and geometric mean antibody titers for pertussis, diphtheria toxin, tetanus toxin, and attenuated poliovirus at 4 weeks after the booster immunization

Rationale

- (1) The assessment was planned to be performed based on an immunological endpoint, in accordance with the “Guidelines for Clinical Studies of Vaccines to Prevent Infectious Diseases”¹⁹⁾ (PFSB/ELD Notification No. 0527-5, issued May 27, 2010). With Hib, it is generally held that an anti-PRP antibody concentration of $1 \mu\text{g/mL}$ is needed for long-term infection prevention,²⁰⁾ and the anti-PRP antibody seroprotection rate at an Hib level of at least $1 \mu\text{g/mL}$ in the primary immunization was therefore established as the primary endpoint. The assessment was planned to be performed based on immunological endpoints for pertussis, diphtheria toxin, tetanus toxin, and attenuated poliovirus, as well, in order to confirm the effects of the addition of the Hib antigen on the efficacy of DTP-IPV.
- (2) 1) The anti-PRP antibody seroprotection rate at an Hib level of at least $0.5 \mu\text{g/mL}$, the level that is considered necessary for preventing Hib infection in the primary immunization, and the geometric mean antibody titer at an Hib antigen level of at least $0.15 \mu\text{g/mL}$, were established as secondary endpoints.
2) Long-term infection prevention through the booster immunization, and the anti-PRP antibody seroprotection rate and geometric mean antibody titer required to prevent infection, were established as secondary endpoints.
3) and 4): The antibody seroprotection rates and geometric mean antibody titers required to prevent pertussis, diphtheria, tetanus, and polio in the primary immunization and secondary immunization were established as secondary endpoints.

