13.3.2.2 Secondary endpoints

- (1) The number and proportion (anti-PRP antibody seroprotection rate) of subjects with an anti-PRP antibody concentration $\geq 0.15 \mu\text{g/mL}$ at 4 weeks after the primary immunization will be calculated.
- (2) The geometric mean antibody titer for anti-PRP antibodies at 4 weeks after the primary immunization will be calculated.
- (3) The number and proportion (anti-PRP antibody seroprotection rate) of subjects with an anti-PRP antibody concentration $\geq 1 \mu\text{g/mL}$ at 4 weeks after the booster immunization will be calculated.
- (4) The number and proportion (anti-PRP antibody seroprotection rate) of subjects with an anti-PRP antibody concentration $\geq 0.15 \mu\text{g/mL}$ at 4 weeks after the booster immunization will be calculated.
- (5) The geometric mean antibody titer for anti-PRP antibodies at 4 weeks after the booster immunization will be calculated.
- (6) The geometric mean antibody titers for pertussis, diphtheria toxin, tetanus toxin, and attenuated poliovirus at 4 weeks after the primary immunization will be calculated.
- (7) The antibody seroprotection rates and geometric mean antibody titers for pertussis, diphtheria toxin, tetanus toxin, and attenuated poliovirus at 4 weeks after the booster immunization will be calculated.

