9. CHANGES TO STATISTICAL ANALYSIS PLAN FROM THE PROTOCOL

Nothing particular

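### Do the 0.5 µg/mL in the protocol's rationale and the differing pertussis and tetanus unit labels leave the seroprotection endpoints undefined?

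*Protocol*

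**What the plan says.** The endpoint list in Protocol 5.3.1 sets the secondary anti-PRP rate at 0.15 µg/mL and names the anti-PRP geometric mean beside it without any limit, both assessed 4 weeks after the third dose. A few lines below, the rationale for that item calls it the "seroprotection rate at an Hib level of at least $0.5 \mu\text{g/mL}$, the level that is considered necessary for preventing Hib infection", and adds that "the geometric mean antibody titer at an Hib antigen level of at least $0.15 \mu\text{g/mL}$, were established as secondary endpoints".

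Protocol 13.3.2.2 gives the analysis. Item (1) is the number and proportion of "subjects with an anti-PRP antibody concentration $\geq 0.15 \mu\text{g/mL}$ at 4 weeks after the primary immunization will be calculated". Item (2) reads "The geometric mean antibody titer for anti-PRP antibodies at 4 weeks after the primary immunization will be calculated", with no lower limit on the titers that enter the mean.

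The pertussis cut-off (PT and FHA) is 10.0 U/mL in Protocol 10.1 and 10.0 EU/mL in SAP Table 4.2. The tetanus cut-off is 0.01 U/mL in the protocol and 0.01 IU/mL in the SAP. Under "CHANGES TO STATISTICAL ANALYSIS PLAN FROM THE PROTOCOL", SAP section 9 records nothing.

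**The concern.** A cut-off and its unit decide which infants count as seroprotected. At first sight there are two anti-PRP cut-offs, 0.15 and 0.5 µg/mL, for one endpoint, and the sentence that justifies the endpoint names the one the analysis does not use. Read literally, the same sentence also confines the geometric mean to titers of at least 0.15 µg/mL. A mean taken only over responders is biased upward and is a different quantity from a mean over all evaluable infants.

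The unit labels look more serious because the pertussis and tetanus rates are part of the primary endpoint. If U, EU and IU were different scales, the protocol and the SAP would apply different thresholds, and the SAP would have made the change without declaring it. The protocol expects the results to be read beside the subcutaneous study BK1310-J01, where differing definitions would mislead.

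**Working it through.** **1. Where each anti-PRP definition appears**

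| Place | Secondary cut-off (µg/mL) | Geometric mean |
|---|---|---|
| Protocol synopsis 7.1 | 0.15 | unrestricted |
| Protocol 5.3.1, endpoint list | 0.15 | unrestricted |
| Protocol 5.3.1, rationale (2) 1) | 0.5 | tied to 0.15 |
| Protocol 10.1 | 0.15 (with a citation) | – |
| Protocol 13.3.2.2 | 0.15 | unrestricted |
| SAP 3.1 | 0.15 | unrestricted |
| SAP 4.2 | 0.15 | unrestricted |
| SAP 7.5.2.1 | 0.15 | – |
| SAP 7.5.2.2 | – | unrestricted |
| SAP section 11, Table 14.2.2.1 | 0.15 | – |

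The value 0.5 occurs once as an antibody level, without a citation, in explanatory text. The SAP never uses it as a cut-off, so the two documents define the same anti-PRP endpoint.

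**2. The geometric mean.** The rationale speaks of an Hib antigen level, not an antibody titer, so the sentence is garbled whichever way it is read. SAP 6.3 sets titers below the limit of quantitation to half that limit. A rate at 0.15 µg/mL can be counted only if the assay quantifies down to 0.15, so every anti-PRP value below the limit also lies below 0.15. A restricted mean would discard all of them, and the SAP rule would have no effect on anti-PRP. The rule makes sense only for an unrestricted mean.

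**3. What would be at stake if the sentence were followed.** The documents give no anti-PRP mean or spread, so these inputs are assumptions: log-normal titers, geometric mean (GM) 1.5 to 10 µg/mL, log10 SD 0.5 to 0.8.

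Share at or above c = Φ((log10 GM − log10 c) / SD).

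- GM 3, SD 0.65, c = 0.15: (0.477 + 0.824) / 0.65 = 2.00, giving 97.7%.
- GM 3, SD 0.65, c = 0.5: (0.477 + 0.301) / 0.65 = 1.20, giving 88.4%. The gap is 9.3 points, or 0.093 × 30 = 2.8 infants.
- Smallest gap, GM 10, SD 0.5: 100.0% and 99.5%, or 0.5 points.
- Near the largest gap, GM 1.5, SD 0.65: 93.8% and 76.9%, or 16.9 points.

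Lowering the GM to 1 with SD 0.6 gives 91.5% and 69.2%, or 22.3 points.

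Restricted mean, on the log10 scale = m + SD·φ(a) / (1 − Φ(a)), with m = log10 GM and a = (log10 0.15 − m) / SD.

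- GM 3, SD 0.65: a = −2.00, and the mean rises from 3.0 to 3.26.
- GM 1.5, SD 0.8: a = −1.25, and the mean rises from 1.5 to 2.19.

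These figures compare the planned analysis with one that no analysis section contains. They show why a real conflict would matter, not an error the trial will make.

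**4. Units.** Pertussis: 10.0 by ELISA in both documents. Tetanus: 0.01 by indirect agglutination in both. A change of scale would normally bring a converted number, whereas an unchanged number under a new label is what relabelling looks like. The analyst compares the value reported by the antibody laboratory with 10.0 or 0.01. The result is the same under either label if the labels name one scale.

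**5. The plan's own figures.** None bears on these cut-offs. The 83% in Protocol 6.1 is 1 − 0.942^30 = 0.833 for a 5.8% adverse-event incidence, and it does not involve them.

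**The case for a change.** The best case for a change rests on the units. They belong to the primary endpoint, and Protocol 10.1 prints IU/mL for diphtheria but U/mL for tetanus in the same table, so loose notation is not an obvious explanation. Neither document states that the labels are equivalent, and SAP section 9 is silent. Estimation is the whole output of this trial, which is meant to support intramuscular use, and a correction would cost a few words. The rationale sentence is also plainly wrong: it leaves the 0.15 µg/mL cut-off without a justification in the section meant to supply one.

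The textual observations stand: the sentence is in error and the labels differ. The consequence does not follow. Protocol 10.1 supplies a citation for 0.15 µg/mL, so the cut-off is not unsupported. Nothing in the documents suggests that the pertussis or tetanus scale changed between protocol and SAP. The comparison with BK1310-J01 cannot carry the point either: that study's cut-offs and units are not given here, and the SAP specifies no analysis against it.

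**Conclusion.** The concern does not hold as a problem with the planned analysis. The anti-PRP part is a clerical slip in one explanatory sentence. All operative text agrees on 0.15 µg/mL and on an unrestricted geometric mean, and the primary anti-PRP cut-off of 1 µg/mL is consistent throughout. The effect on the planned anti-PRP results is nil.

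For pertussis and tetanus, no numeric effect is shown. That conclusion assumes that U and EU, and U and IU, name the same scale for the assays used. The documents neither state nor contradict this, though the identical numbers and methods favour it. Should the assumption prove wrong, Listing 16.2.4 sets out antibody titers for all enrolled subjects, so rates could be recalculated at any threshold.

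The study is exploratory and descriptive, with 30 infants, no tests and no success criterion, so no decision rule depends on the wording. The sentence and labels could be tidied at a later revision, but the results would be the same with or without that edit.
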